4.4 Randomization/Stratification (Cycle 2)

4.4.1 Randomization. Participants will not be randomized at Cycle 1. Randomization will occur following the assessment of CINV after Cycle 1, and a participant will be randomized for Cycle 2 only if the reported nausea at Cycle 1 was ≥ 3 (on a 1-7 scale). A computer-generated randomization schedule will be used to assign participants in equal numbers to the three study arms, with a random (50/50) block of 3 or 6. The schedule is prepared by and maintained by the URCC NCORP Research Base biostatistician.

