8.6 Blinding and Unblinding Methods

Participants, study coordinators, and investigators will be blinded to prochlorperazine/placebo group and the olanzapine/placebo group assignments. Study agents supplied to NCORPs will be labeled with a letter code that will be used to identify the assigned treatment arm for unblinding purposes. An unblinding key will be kept by IDS.

Unblinding of the study agent is ONLY permitted in the case of serious and unexpected adverse events that are definitely, probably or possibly associated with the use of the study agent AND if knowledge of the study treatment arm received is necessary for interpreting the medical event and related treatment of that medical event. In such cases, the treating M.D. or their designee can be given the treatment group assignment from the University of Rochester Investigational Drug Service. Documentation should be sent to the email address below and include participant ID number, site investigator, and reason for unblinding in the message:

[name]
[contact]
[contact]

Participants that require emergency study agent disclosure will discontinue the study agent. The research team may continue to follow the study participant for assessment data with participant and treating physician approval.

8.7

URCC16070 Protocol Version Date 01/04/2023

URCC16070 Protocol Version Date 01/04/2023

Page 33 of 59

URCC16070 Protocol Version Date 01/04/2023

URCC16070 Protocol Version Date 01/04/2023

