14.2 Data Handling

Data will be analyzed as intent-to-treat. The assumptions underlying all statistical analyses will be thoroughly checked using appropriate graphical and numerical methods.(42,43) In the case of serious violations of the assumptions, appropriate nonparametric methods or transformations will be attempted.(44,45) In the event of outlying observations, we will carefully check the data and make corrections if necessary. If no errors are found, we will conduct analyses both with and without the outlying data and report both results to assess the sensitivity. All hypothesis testing will be performed at the two-sided 0.05 level, with the exception of the Primary Analysis, which will use the 0.05/2=0.025 level. SAS, JMP and R will be used for the analyses as appropriate.

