14.3 Sample Size and Power

Sample Size: The number of participants needed for the randomized portion of the study will be 111 participants per arm, or 333 total. The accrual necessary at Cycle 1 to have 333 eligible participants for the randomized portion of the trial at Cycle 2 will be 1600. These numbers are derived based upon data from Preliminary Study 2. In that study, 46.1% of the randomized participants reported Peak Nausea of ≥ 3 , the nausea eligibility criterion for this study. Using that number, in order to have 333 eligible participants at Cycle 2, we will need to accrue 724 participants at Cycle 1. We conservatively assume that 10% of the Cycle 1 participants who would be eligible for the randomized portion of the study at Cycle 2 will decide not to continue with the study, so we will increase our targeted accrual at Cycle 1 by 10% to 796 participants. We rounded this number to 800 for our projected recruitment at Cycle 1 and will recruit additional participants beyond the projected 800, if necessary, to reach our Cycle 2 target of 333 randomized participants. In summary, we anticipate approximately 28% of patients screened during Cycle 1 to enroll for the randomized portion of the study. Eligible patients willing to continue on the study, will be immediately following the assessment of CINV after Cycle 1 of chemotherapy randomized to continue on the study. Randomized portion of the study starts at Cycle 2 of chemotherapy. Following URCC Research Base standard operation procedures, data are evaluated for quality immediately upon its receipt. Moreover, the statistical group routinely performs data quality checks to identify problems so corrective action can be taken early. Therefore, we anticipate the data analysis to begin 4-6 weeks after full enrollment is completed and data has matured.

Update 04/29/2020: Based on the first 517 subjects, 214 were eligible for Cycle 2 for 41.4%, falling slightly below of our preliminary estimate of 46.1%. Of the 214 subjects eligible for Cycle 2, only 135 (63%) decided to continue with the study. We had assumed a maximum of 10% would not continue with the study, while in reality 37% of subjects did not continue the study. Therefore, it is necessary to increase our Cycle 1 accrual to 1,200 subjects in order to meet our Cycle 2 target of 333 randomized participants, as the majority of our statistical assumptions are based on that sample size.

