Update 08/01/2022: Based on the first 1,084 subjects, 413 were eligible for Cycle 2 for 39.0%, falling slightly below of our preliminary estimate of 41.1%. Of the 413 subjects eligible for Cycle 2, only 241 (58%) decided to continue with the study. We had assumed a maximum of 10% would not continue with the study, while in reality 42% of subjects did not continue the study. Therefore, with recruiting 1500 patients for Cycle 1, it is expected on average (probability 50%) that $=333$ will enroll for Cycle 2. To ensure high probability to reach the targeted goal $n=333$ for Cycle 2, we propose to recruit $n=1600$ for Cycle 1. Recruiting $n=1600$ patients for Cycle 1 provides 90% probability to meet our Cycle 2 target of 333 randomized participants, as the majority of our

statistical assumptions are based on that sample size.

Power: Our target accrual of evaluable participants for the randomized portion of the study is 100 participants per arm. We conservatively assume that 10% of randomized participants will fail to provide evaluable data so we will recruit 111 participants per arm, or 333 total. The standard deviation and pre-post correlation for average nausea at cycle 2 for 35 participants in an ongoing R01 examining acupressure bands in addition to standard antiemetics in breast cancer patients beginning chemotherapy who had nausea of ≥ 3 at cycle 1 and provided data at cycle 2 and did not use acupressure bands were 0.953 and 0.5, respectively.

For the Primary aim, we will use a one-way analysis of variance on Post – Pre change scores. We have Arms 1 (control), 2, and 3. Two tests will be done using contrasts: 1 vs. 2 and 1 vs. 3, and a significance level of $0.05 / 2 = 0.025$. Using the numbers above, we estimate the SD of the change scores to be 0.953, conservatively assuming a pre-post correlation of 0.5. When the sample size in each of the 3 groups is 100, we calculate that our planned one-way analysis of variance will have 90% power to detect a difference in means of 0.48, or a half standard deviation. In light of the fact that there are no minimum clinically important difference (MCID) guidelines for changes in our average nausea measure, this can be considered to be a clinically relevant change.(46)

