14.5 Primary Objectives and Analysis Plans

14.5.1 The **Primary Aim** is to determine if control of nausea at Cycle 2 in participants who experienced CINV at Cycle 1 is improved by the addition of either prochlorperazine or olanzapine to the control arm of netupitant, palonosetron and dexamethasone.

14.5.2 **Primary Hypothesis:** Control of nausea at Cycle 2 in participants who experienced CINV at Cycle 1 despite receiving ASCO-recommended antiemetics(1) can be improved by the addition of either prochlorperazine or olanzapine to the standard antiemetic combination of netupitant, palonosetron and dexamethasone.

14.5.3 **Primary Analysis:** We will use a one-way analysis of variance on Post – Pre change scores. We have Arms 1 (control), 2, and 3. Two tests will be done using contrasts: 1 vs. 2 and 1 vs. 3, using a significance level of $0.05 / 2 = 0.025$.

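### Optional gain, not an error: Holm's step-down rule for the two primary contrasts would keep the 5% familywise limit and every Bonferroni rejection, and add some power for the second drug

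*Combined protocol and SAP*

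**What the plan says.** The primary analysis (14.5.3) is a one-way analysis of variance on change scores with two contrasts against the control arm: "Two tests will be done using contrasts: 1 vs. 2 and 1 vs. 3, using a significance level of" 0.05/2 = 0.025. Section 14.2 gives the same level: "All hypothesis testing will be performed at the two-sided 0.05 level, with the exception of the Primary Analysis, which will use the 0.05/2=0.025 level". Section 14.3 computes power at that level and reports, for 100 evaluable participants per arm, that "our planned one-way analysis of variance will have 90% power to detect a difference in means of 0.48". The three sections agree, and none attaches a step-down rule.

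For the primary contrasts, only the general rule in 14.2 indicates two-sided testing. Section 14.6.1 does specify a one-sided test, but for olanzapine against prochlorperazine, which is not a primary contrast.

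The primary aim (14.5.1) asks whether nausea control is "improved by the addition of either prochlorperazine or olanzapine to the control arm".

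Two later sections lean on the primary rule. Section 14.6.2 applies the same contrasts to vomiting at 0.025, and 14.7.2 has the FACT-G analysis follow the primary procedures.

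**The concern.** Under single-step Bonferroni the second contrast stays at 0.025 even after the first has been rejected. Suppose one drug clearly beats control and the other has p = 0.03. The plan does not declare the second drug effective, although a 5% familywise limit would allow that claim. Each drug has its own contrast and so its own verdict. Section 2 describes olanzapine as having the more problematic side-effect profile of the two, so knowing separately whether each drug works is useful. What is at stake is some power for the second drug at the same sample size, not the validity of the trial.

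**Working it through.** **Inputs.** From 14.3: difference 0.48, SD of change scores 0.953, 100 evaluable per arm. From 14.2 and 14.5.3: 0.025 per contrast. From 4.4.1: equal allocation. The three-arm error degrees of freedom are 300 − 3 = 297.

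**1. The plan's own power.** Standard error of a contrast = 0.953 × √(2/100) = 0.1348. Noncentrality = 0.48 / 0.1348 = 3.56. The two-sided critical t at 0.025 with 297 df is 2.253. Noncentral t power is 90.4% (90.7% by the normal approximation), which reproduces the stated 90%. One-sided 0.025 would give 94.5% by the normal approximation, which does not match. The two-sided reading is therefore the one consistent with the plan's own figure.

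**2. Why Holm stays within 5%.** If both drugs are ineffective, a false claim requires the smaller p-value to be at most 0.025, which has probability at most 2 × 0.025 = 0.05. If one drug is ineffective, a false claim requires its own p-value to be at most 0.05. Both bounds hold under any dependence, so the shared control arm is no obstacle. A contrast rejected at 0.025 under Bonferroni is also rejected under Holm.

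**3. Size of the gain.** Simulation of 2,000,000 trials per scenario, with shared control, pooled variance and 297 df:

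| Both effects 0.48 | Bonferroni | Holm |
|---|---|---|
| Power per drug | 90.4% | 93.4% |
| Both drugs shown | 83.9% | 89.9% |
| At least one shown | 96.9% | 96.9% |

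The figures are coherent. At least one = 90.4 + 90.4 − 83.9 = 96.9. Each changed verdict turns one claim into two, so the 3.0-point gain per drug, counted for two drugs, equals the 89.9 − 83.9 = 6.0% of trials whose verdict changes.

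The documents give only 0.48 as an effect. If the second drug is assumed weaker while the first has 0.48, its power rises from 32.0% to 42.2% at an assumed effect of 0.24, and from 66.2% to 74.7% at 0.36.

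**4. Where the added claims lie.** Smallest significant observed difference at SD 0.953:
- at 0.025: 2.253 × 0.1348 = 0.304
- at 0.05: 1.968 × 0.1348 = 0.265

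Added claims therefore have observed differences between about 0.265 and 0.304, which is 55% to 63% of 0.48. (The band shifts with the SD actually observed.)

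**5. Error cost.** With both drugs null, familywise error is 4.6% under both rules. With one drug null and the other at 0.48, the chance of falsely claiming the null drug rises from 2.5% to about 4.5%. It reaches 5.0% at most, when the other effect is very large. In every scenario, no Bonferroni rejection was lost under Holm.

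**6. Intervals.** Take p = 0.03 for the second drug at SD 0.953. The difference is 0.294, the 97.5% interval is −0.010 to 0.598, and the 95% interval is 0.029 to 0.559. A 97.5% interval includes zero whenever Holm adds a claim. A 95% interval can exclude zero without a Holm claim, in about 1.6% of trials at the design values.

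**The case against.** The strongest objection is that there is no defect. The rule is valid, consistent across sections, meets its stated power and comes with simple matching intervals, so Holm is only a preference. The first part stands. A reader might infer that the multiplicity control is faulty or that the trial is underpowered for its primary contrasts; the documents support neither. Holm is more than a preference, though, because it never loses a claim that Bonferroni makes and stays within the same limit.

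The practical value can also be questioned. Every added claim at SD 0.953 rests on an observed difference below the 0.48 that 14.3 treats as clinically relevant. That stands and limits the point. So does the ambiguity of either in the primary aim: read as at least one, the gain is zero.

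Holm is not the only alternative. A Dunnett-type critical value (about 2.22 against 2.253) would use the shared control and help the first test too. In the scenarios run, step-down Dunnett adds less than one point per drug beyond Holm. Holm needs no special critical value.

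The last objection is timing. At the 08/01/2022 update, of those eligible "only 241 (58%) decided to continue with the study", which is 241/333 = 72% of the target, and the protocol footer reads "URCC16070 Protocol Version Date 01/04/2023". Changing a primary decision rule this late invites questions about motive. On randomization, 4.4.1 states: "The schedule is prepared by and maintained by the URCC NCORP Research Base biostatistician". Section 14.3 adds that "the statistical group routinely performs data quality checks to identify problems so corrective action can be taken early". Section 8.6 lists participants, coordinators and investigators as blinded and does not mention statisticians. A reader might infer that outcomes by arm have been seen. The documents do not say so, and 14.8 plans no interim analysis. Equally, they do not establish that outcomes are unseen. This part of the objection stands as a condition on the fix.

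**Conclusion.** A cheap improvement, not an error. No stated sample size or power figure is wrong. At the design values (both effects 0.48, SD 0.953, 100 per arm, two-sided 0.025), Holm adds 3.0 points of power per drug and 6.0 points for showing both, and nothing for showing at least one. The gain is larger if one drug is weaker, but those smaller effects are assumptions. The conclusion rests on two readings: that the primary 0.025 is two-sided, which the power check supports, and that a separate verdict on each drug is wanted, which the wording of the aim does not settle. The price is a higher false-claim risk for a single ineffective drug, within the 5% familywise limit, and the loss of equally simple matching intervals.

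**What to change.** In 14.5.3, and by reference in 14.2 and 14.3, write:

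> The two primary contrasts (1 vs. 2, 1 vs. 3) are tested by the Holm procedure at familywise two-sided 0.05: the smaller p-value at 0.025 and, only if significant, the larger at 0.05.

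In the same amendment:
- **14.6.2:** apply the same Holm rule to the two contrasts with control for vomiting, or state that they stay at single-step 0.025. Otherwise the same contrasts would follow different rules without explanation.
- **14.7.2:** state which rule the FACT-G analysis inherits.
- **Intervals:** report either 97.5% intervals, labelled as single-step Bonferroni intervals that do not define the Holm decision, or 95% intervals, labelled as not adjusted for multiplicity.

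The sample size is unchanged, and the stated 90% per contrast becomes a lower bound. The cost is a few sentences and a late protocol amendment, which under 15.1 goes through DCP and needs CIRB approval before it takes effect. Make the change only if it is documented beforehand that outcomes by arm are unseen by those proposing it; otherwise keep Bonferroni as written.

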14.6 Secondary Objectives, Endpoints, Analysis Plans

14.6.1 **Secondary Aim 1** is to determine if olanzapine is more effective than prochlorperazine in controlling nausea at Cycle 2 in participants who experienced CINV at Cycle 1 when used in combination with netupitant, palonosetron and dexamethasone. This will be assessed by estimating the contrast $D = (3 - 1) - (2 - 1)$, where 3 is the Arm 3 mean, 2 is the Arm 2 mean, and 1 is the Control mean, and testing whether $D = 0$ versus the one-sided alternative hypothesis that $D > 0$.

14.6.2 **Secondary Aims 2 and 3** will compare the effects of the interventions on vomiting

by fitting a generalized linear model. The response will be Any Vomiting (yes/no) after Cycle 2, treatment arm as the main factor, and Any Vomiting after Cycle 1 as a covariate. Estimation will be performed using maximum likelihood assuming a binomial distribution and logit link. The same group of contrasts described in the Primary Aim analysis will be estimated and tested, with a significance level of 0.025 to adjust for multiple tests.

14.7 Exploratory Analyses:

14.7.1 We will create an empirically-based algorithm predicting nausea from breast cancer chemotherapy regimens. To do so, we will use the Cycle 1 diary data (total N = approximately 1600 overall) to develop a predictive model for the risk of developing nausea, using age, race, ethnicity, QOL, alcohol consumption, susceptibility to nausea, expectancy, anxiety, level of nausea on the day prior to treatment, and prior history of nausea as potential predictors. For this analysis, the outcome will be binary, with Nausea=YES if Peak Nausea ≥ 3 and NO otherwise. We will apply two modeling paradigms: 1) Classification Trees, and 2) logistic regression.

14.7.1.1 Classification trees consist of finding a series of binary rules with which to base classifications, e.g., if Age is under 65, Race is Caucasian, and highly emetogenic chemotherapy agents are used, there is a X% risk of CINV. These models are very easy to apply in practice and have been shown to be especially effective if there are interactions between the predictors in the model.(47) We will use Conditional Tree methodology for the computations.(48)

14.7.1.2 Logistic regression will also be performed. This method can be superior to classification trees if there are few, if any, interactions among the predictor variables. The best model will be chosen using leave-one-out cross validation, where an observation is set aside; the model is fit to the remaining ones, and the fitted model is used to predict the set-aside observation. This is repeated for each observation. The resultant set of predictions is compared to the observed data in terms of misclassification rate, sensitivity, specificity and area under the curve.

14.7.2 We will compare the effects of the interventions on QOL, as assessed by the FACT-G, by following the same procedures described under the Primary Aim and the first Secondary Aim, using change in the FACT-G scores as the response.

14.7.3 Descriptive analyses will be conducted on the frequency and severity of side-effects, i.e., sleep disturbance, fatigue, anxiety, and dizziness, across treatment conditions.

14.7.4 Assessment of biological factors (e.g. GSH recycling, genetic markers) may help identify a subgroup of patients at high risk for development of cancer-related or treatment-related side effects, or response to treatment. Assays to investigate these factors may include, for example, measurement of GSH metabolism, assessment of genetic variants such as SNPs, measurement of cytokines, or measurement of proteins associated with drug absorption, distribution, metabolism, and excretion. The most promising assay(s) will be selected at the time of analysis based on the current state of the science.

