2. AIMS/OBJECTIVES

2.1 Primary Aim is to determine if control of nausea at Cycle 2 in participants who experienced CINV at Cycle 1 is improved by the addition of either prochlorperazine or olanzapine to the control arm of netupitant, palonosetron and dexamethasone.

2.1.1 Hypothesis 1: Control of nausea at Cycle 2 in participants who experienced CINV at Cycle 1 despite receiving an ASCO-recommended antiemetics(1) can be improved by the addition of either prochlorperazine or olanzapine to the standard antiemetic combination of netupitant, palonosetron and dexamethasone.

2.2 Secondary Aim 1 is to determine if olanzapine is more effective than prochlorperazine in controlling nausea at Cycle 2 in participants who experienced CINV at Cycle 1 when used in combination with netupitant, palonosetron and dexamethasone.

2.2.1 Hypothesis 2: Olanzapine, which is a newer antiemetic drug with a more problematic side-effect profile than prochlorperazine, is more effective than prochlorperazine in controlling nausea when used in combination with netupitant, palonosetron and dexamethasone.

2.3 Secondary Aim 2 is to determine if control of vomiting at Cycle 2 in participants who experienced CINV at Cycle 1 is improved by the addition of either prochlorperazine or olanzapine to the control arm of netupitant, palonosetron and dexamethasone.

2.3.1 Hypothesis 3: Control of **vomiting** at Cycle 2 in participants who experienced CINV at Cycle 1 despite receiving an ASCO-recommended antiemetic regimen(1) can be improved by the addition of either prochlorperazine or olanzapine to the standard antiemetic combination of netupitant, palonosetron and dexamethasone.

2.4 Secondary Aim 3 is to determine if olanzapine is more effective than prochlorperazine in controlling vomiting at Cycle 2 in participants who experienced CINV at Cycle 1 when used in combination with netupitant, palonosetron and dexamethasone.

2.4.1 Hypothesis 4: Olanzapine, which is a newer antiemetic drug with a more problematic side-effect profile than prochlorperazine, is more effective than prochlorperazine in controlling **vomiting** when used in combination with netupitant, palonosetron and dexamethasone.

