7.2 Secondary Endpoints

The outcome variable for secondary aim 1 will be average nausea as described above. The outcome variable for secondary aims 2 and 3 will be Any Vomiting (yes/no).

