14.4 Calculation of the Primary Outcome Variable

The primary outcome variable will be Average Nausea (measured on a 7-point scale anchored by “Not at all Nauseated” and “Extremely Nauseated”) defined as the average nausea rating across 15 assessment points (i.e., the afternoon, evening, and night reporting periods on Day 1 and the morning, afternoon, evening, and night reporting periods on Days 2 – 4. In the event that data are missing from eleven or more of the fifteen nausea assessment points, we will set the score to missing.

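### Secondary Aim 1 tests olanzapine against prochlorperazine in the wrong direction, and its one-sided form conflicts with Section 14.2

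*Combined protocol and SAP*

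**What the plan says.** Section 2.2.1 (Hypothesis 2) states the expected direction: "Olanzapine, which is a newer antiemetic drug with a more problematic side-effect profile than prochlorperazine, is more effective than prochlorperazine in controlling nausea".

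Section 14.6.1 turns this into a test. It defines D = (3 - 1) - (2 - 1), where the digits stand for arm means (1 control, 2 prochlorperazine, 3 olanzapine), and tests D = 0 "versus the one-sided alternative hypothesis that" D > 0. It gives no significance level.

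On the outcome, Section 7.2 says: "The outcome variable for secondary aim 1 will be average nausea as described above". Section 14.4 describes that score as "measured on a 7-point scale anchored by" no nausea at one end and extreme nausea at the other. For the primary aim, Section 14.5.3 says: "We will use a one-way analysis of variance on Post – Pre change scores".

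On sidedness, Section 14.2 says: "All hypothesis testing will be performed at the two-sided 0.05 level, with the exception of the Primary Analysis". That exception moves the level to 0.025; it does not introduce one-sided testing. Section 14.6.2 (vomiting) departs from 14.2 openly, giving 0.025 and the reason, multiple tests. Section 14.7.2 reuses the primary and first secondary procedures for change in FACT-G.

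**The concern.** There are two separate faults. First, the alternative hypothesis points the wrong way: a positive D means more nausea, or less improvement, on olanzapine. Second, a one-sided test contradicts the general rule in 14.2, and nothing in 14.6.1 explains the departure.

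This is the only planned head-to-head comparison of the two drugs on nausea. Followed to the letter, it gives a p-value near 1 when olanzapine works better and can declare significance when it works worse. In practice the estimate of D would reveal the direction and someone would notice. The likelier harm is that the tail, or the choice between one and two sides, is then settled after the results are known.

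**Working it through.** **Inputs.** 100 evaluable participants per arm, SD of the cycle 2 score 0.953 and pre-post correlation 0.5 (Section 14.3). The plan gives no olanzapine-versus-prochlorperazine difference, so I assume 0.48 (borrowed from the primary contrasts), with 0.36 and 0.24 as a range. Section 14.6.1 gives no alpha, so I assume one-sided 0.05.

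**1. The plan's own power figure.**
- SD of change = 0.953 × √(2 × (1 - 0.5)) = 0.953.
- SE of a difference between two arms = 0.953 × √(2/100) = 0.1348.
- Error df = 300 - 3 = 297.
- For 0.48 the non-centrality is 0.48 / 0.1348 = 3.562. At two-sided 0.025 the non-central t gives 90.4% power.

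Section 14.3 claims "90% power to detect a difference in means of 0.48, or a half standard deviation", so the inputs reproduce the plan.

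**2. The sign of D.** The control mean cancels: D = (3 - 1) - (2 - 1) = Arm 3 mean - Arm 2 mean, that is, olanzapine minus prochlorperazine.

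Higher scores are worse. The anchors in 14.4 run from none to extreme. Section 4.4.1 says "a participant will be randomized for Cycle 2 only if the reported nausea at Cycle 1 was" at least 3 on the 1-7 scale, and Section 14.1 calls that population moderate or greater in nausea.

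Example: with changes of -0.50, -0.80 and -1.28 in Arms 1, 2 and 3, olanzapine is better by 0.48, and D = (-1.28 + 0.50) - (-0.80 + 0.50) = -0.78 + 0.30 = -0.48. Raw Cycle 2 scores give the same sign. Hypothesis 2 is D < 0.

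**3. What the written test does.** Non-central t, 297 df, non-centrality 1.781, 2.671 and 3.562:

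| True difference | 0.24 | 0.36 | 0.48 |
|---|---|---|---|
| Written test rejects, olanzapine better | 0.0003 | 0.000008 | 0.0000001 |
| Written test rejects, olanzapine worse | 55% | 85% | 97.2% |
| Power, one-sided 0.05 in the correct tail | 55% | 85% | 97.2% |
| Power, two-sided 0.05 | 43% | 76% | 94.4% |

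A simulation of 20,000 trials with D = -0.48 agrees: no rejections as written, 97.3% in the correct tail and 94.7% two-sided. If the one-sided alpha is taken as 0.025, the first row falls further and the second becomes 43%, 76% and 94.4%.

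**4. What remains once the sign is corrected.** Critical |D| is 1.650 × 0.1348 = 0.222 for one-sided 0.05 and 1.968 × 0.1348 = 0.265 for two-sided 0.05. Between them, sidedness alone decides the result. For an observed D of -0.24 (t = -1.781), p is 0.96 as written, 0.038 one-sided in the correct tail and 0.076 two-sided.

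The chance of landing in that band is the difference between the last two rows of the table: 55.2% - 42.7% = 12.5% at 0.24, 84.6% - 75.9% = 8.7% at 0.36, and 97.2% - 94.4% = 2.8% at 0.48.

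**5. FACT-G.** Section 14.7.2 inherits the sidedness conflict. The documents do not state which way FACT-G is scored, so the direction error is not shown to carry over.

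**The case against.** The strongest reply is that this is a sign slip in a secondary aim whose intent is plain. Hypothesis 2 and the opening sentence of 14.6.1 both say in words that olanzapine is expected to be more effective, so an analyst can tell which tail was meant. There is no interim analysis, no other decision in the plan depends on this test, and the estimate of D would show the true direction. All of that is fair, and it makes a literal application of the wrong tail unlikely. It does not settle sidedness, on which 14.2 and 14.6.1 cannot both be followed.

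It can also be said that 14.2 supplies a default 0.05, that 14.6.1 is a specific rule overriding a general one, and that the disputed band is only about 0.04 wide (0.265 - 0.222). The default level is a reasonable reading. But 14.2 names a single exception, and this is not it. The band depends on alpha being 0.05 one-sided; at one-sided 0.025 in the correct tail it essentially disappears. That the answer turns on an unstated alpha is itself a reason to write it down.

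Section 14.6.1 does not name the response whose means it contrasts. If they were means of nausea reduction, D > 0 would be right. No visible text defines the score that way, although parts of the public protocol are blacked out. Section 7.2 points to Average Nausea itself and 14.5.3 to Post – Pre.

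Finally, two-sided testing is not the only remedy. One could reverse the sign, keep the test one-sided, and list it in 14.2 as an exception with its alpha. That would be coherent, but it adds an exception where the plan's existing rule already gives an answer.

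**Conclusion.** Both faults hold. As written, the only planned head-to-head nausea test has an alternative opposite to Hypothesis 2, and its one-sided form contradicts 14.2. Followed exactly, it has essentially no chance of supporting olanzapine when olanzapine is better, and a 55% to 97% chance of rejecting when olanzapine is worse by 0.24 to 0.48. With the direction corrected, the unresolved sidedness would still decide the result in about 3% to 13% of trials over the same range.

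The sign error follows from the definitions alone. The probabilities rest on the plan's 100 per arm and SD of 0.953, and on the assumed differences and one-sided alpha. The primary contrasts, their 90% power and the sample size are not affected. The text must be corrected, because a prespecified test should not need reinterpreting once results are known.

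**What to change.** Replace the test in 14.6.1 with wording such as: *Estimate D as the Arm 3 mean minus the Arm 2 mean in Post – Pre Average Nausea and test D = 0 two-sided at 0.05; D < 0 favours olanzapine.* In 14.7.2, add that the corresponding FACT-G comparison is two-sided at 0.05, and state separately which sign is favourable for FACT-G. Make both changes before unblinded data are seen.

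The cost is one sentence and one clause, through the amendment route in Section 15.1 (DCP submission, then CIRB approval before implementation). Relative to a correctly directed one-sided 0.05 test, power falls by about 3 points at 0.48 (97.2% to 94.4%), 9 at 0.36 and 13 at 0.24. Sample size and data collection do not change.
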